11.1.3.2.2 Assumptions on Missing Data Mechanism

In addition to the extent of missing data, the mechanism under which missing data occur may affect the estimate of the parameter of interest.

The potential impact of missing efficacy endpoints on the estimates of treatment effects will be assessed using alternative statistical models with different underlying assumptions on the missing data mechanism (missing not at random(MNAR)) (Little and Rubin, 1987).

A pattern-mixture model using a treatment-based multiple imputation method (Ratitch et al, 2011) will be used for a sensitivity analysis to explore the robustness of the ANCOVA results for the primary efficacy results.

11.1.3.2.3 PMM –Last Mean Carried Forward

A pattern-mixture model using a last mean carried forward multiple imputation method (Carpenter et al, 2013) will be used as another sensitivity analysis to explore the robustness of the ANCOVA results for the primary efficacy variables. Using this method, missing data after ending Week will be imputed based on the last non-missing mean from its own treatment group.

The steps to implement this sensitivity analysis are as follows. Parameters below refer to the parameters of the multivariate normal distribution for baseline and post baseline Hb measurement.

1. Create posterior distribution of parameters: Separately for each treatment group, take all patients observed data and assuming MAR to fit a multivariate normal distribution with unstructured mean (i.e. a separate mean for each of the baseline plus post-baseline

scheduled weeks and unstructured variance covariance matrix using a Bayesian approach with an improper prior for the mean and an uninformative Jereys' prior for the variance-covariance matrix (Schafer, 1997, p. 155).

2. Draw parameters: Separately for each treatment group, draw variance-covariance matrix from the posterior distribution for the parameters using seed 453628. The mean Vector would be set to the marginal mean for their randomized treatment arm at their last non-missing measurement.
3. Build joint distribution of missing data and observed data: For each subject with missing data, using the draws for the parameter to build the joint distribution of their observed and missing data.
4. Construct conditional distribution of missing data give observed data: For each patient with missing data, use their joint distribution in previous step to construct their conditional distribution of missing given observed outcome data. Sample their missing data from this conditional distribution, to create a “completed” data set, using seed 732545.

Repeat the above steps for 200 times and resulting in 200 imputed data sets. Then fit ANCOVA model for each imputation data set, and combine the resulting parameter estimates and standard errors using Rubin’s rules (Rubin, 1987) for final inference.

11.1.3.2.4 PMM –Baseline Carried Forward (Roxadustat Only and Both Groups)

The analysis is the same as PMM – Last Mean Carried Forward except imputing the missing data. The imputation data will be generated similarly as last mean carried forward method described above but instead of using post-baseline observed data, only baseline data will be used. The similar analyses will be conduct in two scenarios.

- The baseline carried forward imputation will be performed for the roxadustat treatment group only, while for active control group, the imputation data will be generated using the last mean carried forward described above.
- The baseline carried forward imputation will be performed for the both treatment groups.

Similarly, the Rubin’s method will be then used to combine the estimates and the differences between the least square mean differences between the two treatment groups from each of the ANCOVA analysis. This sensitivity analysis will be performed for U.S. primary endpoints only.

11.1.3.3 Logistic Regression

The primary analysis for Ex-US endpoint will also be repeated using logistic regression for PPS population. In addition to the stratification factors except Screening Hb values (≤ 8 g/dL vs. > 8 g/dL) and treatment group, and baseline Hb will be included as continuous covariates. The odds ratio for roxadustat versus placebo and its 95% confidence interval will be provided.

This model will also be repeated using logistic regression and adjusting by sex and age, in addition to the factors mentioned above.

11.1.3.4 Subgroup Analysis

The primary analysis of the US primary endpoint may be repeated separately by sex, age group, geographic region, baseline Hb categories, baseline CRP, baseline iron status, and cardiovascular/cerebrovascular/thromboembolic medical history on ITT Population. The subgroup analysis of the Ex-US primary endpoint may be performed on PPS for non-inferiority and FAS for superiority.

11.2 ANALYSIS OF SECONDARY ENDPOINTS

The secondary endpoints are for both U.S. and Ex-U.S. submission unless otherwise specified. Once the primary hypothesis has been rejected for the primary endpoint, the secondary endpoints in the order that was specified in section 4.3 will be tested using a fixed sequence testing procedure, in order to maintain the overall two-sided type I error of 0.05. If p-value from a test is < 0.05, the claim of superiority or non-inferiority will be considered successful and the test will progress to the next comparison in sequence as follows.

Table 5 Key Secondary Endpoints Fixed Sequence Testing Procedure

Test	Variable	Comparison
1	Proportion of subjects who achieve an Hb response at two consecutive visits during the first 24 weeks of treatment, (U.S.) or the mean Hb change from baseline to the average level during the Evaluation Period, defined as Week 28 until Week 52 for Ex-U.S..	Non-inferiority of roxadustat versus EPO. The non-inferiority margin for the difference of responder analysis between groups is 0.15 The non-inferiority margin for the difference of average of Change in Hb values between groups is - 0.75 g/dL.
2	LDL cholesterol change from BL to the average of weeks 12 to 24.	Superiority of roxadustat versus EPO
3	Mean change from baseline in Hb levels between Weeks 18 to 24 in patients whose baseline CRP > ULN:	The non-inferiority with margin of - 0.75 of roxadustat versus EPO
4	Monthly IV iron (mg) use per subject during weeks 28 to 52.	Superiority of roxadustat versus EPO
45	Time to first RBC transfusion during the treatment.	Non-inferiority of roxadustat versus EPO with Non-inferiority margin of 1.8
5	Change from BL to the average MAP of weeks 8 to 12	Superiority of roxadustat versus EPO
6	Time to first exacerbation of hypertension (defined as [systolic BP \geq 170 mmHg AND systolic BP increase from BL \geq 20 mmHg] or [diastolic BP \geq 110 mmHg AND diastolic BP increase from BL \geq 15 mmHg]) during weeks 28 to 52	Superiority of roxadustat versus EPO & Non-inferiority with margin of 1.8

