### 7.2 Secondary Endpoints

- **US (FDA) submission:** The proportion of subjects who achieve a Hb response at two consecutive visits during the first 24 weeks of treatment, without rescue therapy within 6 weeks prior to the Hb response.

A Hb response is defined, using central laboratory values, as

- Hb  $\geq 11.0$  g/dL and a Hb increase from baseline by  $\geq 1.0$  g/dL in subjects whose baseline Hb  $> 8.0$  g/dL, or
- Increase in Hb  $\geq 2.0$  g/dL in subjects whose baseline Hb  $\leq 8.0$  g/dL

- **Ex-US submission:** Mean Hb change from baseline to the average level during the Evaluation Period, defined as Week 28 until Week 36 without rescue therapy within 6 weeks prior to and during the evaluation period. This analysis will be based on the PPS population.

Both, US and ex-US Submissions:

- Average monthly IV iron use per subject during the Treatment Period. Mean change in low-density lipoprotein (LDL) cholesterol averaged over Weeks 12 to 24.

- Blood pressure effects:
  - Proportion of subjects with exacerbation of hypertension, meeting at least one of the following criteria:
    - Increase in BP: An increase from baseline of  $\geq 20$  mm Hg systolic BP and sBP  $>170$  mmHg, or an increase from baseline of  $\geq 15$  mm Hg diastolic BP and dBP $>100$  mmHg. Increases from baseline in blood pressure must be confirmed by repeat measurement.
  - Time to an increase in BP as defined above.
  - Mean change in mean arterial pressure (MAP) averaged over Weeks 8 to 12.
- Time to achieve first Hb response as defined by the primary endpoint (ex-US) (which is the secondary endpoint for the US [FDA]).

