This efficacy endpoint will be analyzed using a mixed model of repeated measures (MMRM) with Hb baseline value as covariate and treatment group and randomization stratification factors as fixed effects and MI ANCOVA as sensitivity analysis for Ex-US submission.

This null hypothesis will be rejected if the two-sided 95% CI for the difference of least square means from the mixed model is above -0.75 g/dL.

Hb values under the influence of a rescue therapy within 6 weeks prior to and during this 8-week evaluation period will be censored in the analysis.

- The average monthly iron use will be compared between the 2 treatment groups using an ANCOVA model with baseline iron replete as a covariate, and treatment group and randomization stratification factors as fixed effects. Superiority will be declared if the lower bound of the two-sided 95% CI of the difference between epoetin alfa and roxadustat exceeds zero.
- Mean change from baseline in LDL cholesterol averaged over Weeks 12 to 24 will be analyzed using an MMRM model with baseline LDL cholesterol as a covariate and treatment group, visit, visits by treatment arm, and randomization stratification factors as fixed effects. Superiority will be declared if the lower bound of the two-sided 95% CI of the difference between epoetin alfa and roxadustat exceeds zero.

- Proportion of subjects with exacerbation of hypertension, meeting at least 1 of the following criteria will be analyzed using CMH model adjusting for treatment group and stratification factors
  - Increase in blood pressure: An increase from baseline in systolic blood pressure (sBP) of  $\geq 20$  mm Hg and sBP  $> 170$  mmHg or an increase from baseline in diastolic blood pressure (dBP) of  $\geq 15$  mm Hg and dBP  $> 100$  mmHg. Increases from baseline in blood pressure must be confirmed by repeat measurement.

Noninferiority of roxadustat vs. epoetin alfa will be tested. Non-inferiority will be declared if the upper bound of the two-sided 95% CI of the hazard ratio is less than 1.3.

- Time to an increase in blood pressure (defined as an increase from baseline of  $\geq 20$  mm Hg systolic BP and sBP  $> 170$  mmHg or an increase from baseline of  $\geq 15$  mm Hg diastolic BP and dBP  $> 100$  mmHg). Time to an increase in blood pressure will be analyzed using the Cox Proportional Hazards model adjusting for treatment group and randomization stratification factors. Superiority of roxadustat vs. epoetin alfa will be tested.

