4.3 SECONDARY EFFICACY ENDPOINTS

The secondary efficacy endpoints are for both US and Ex-US submissions unless specified otherwise:

US (FDA submission): The proportion of subjects who achieve a Hb response at two consecutive visits with at least 5 days apart during the first 24 weeks of treatment, without rescue therapy within 6 weeks prior to the Hb response. This analysis will be based on the ITT Population.

A Hb response is defined, using central laboratory values, as

- Hb ≥ 11.0 g/dL and a Hb increase from baseline by ≥ 1.0 g/dL in subjects whose baseline Hb > 8.0 g/dL, or
- Increase in Hb ≥ 2.0 g/dL in subjects whose baseline Hb ≤ 8.0 g/dL

Ex-US submission: Mean Hb change from baseline to the average level during the Evaluation Period, defined as Week 28 until Week 36 without rescue therapy within 6 weeks prior to and during the evaluation period. This analysis will be based on the PPS population.

- The time to achieve the first hemoglobin (Hb) response defined by the primary endpoint for Ex-US or the first secondary efficacy endpoint for the US submission.
- Proportion of patient exposure time (months) with Hb ≥ 10 g/dL during Weeks 28-52, similarly analysis for the period between Weeks 28 - 36
- Mean change from baseline in Low-density lipoprotein (LDL) cholesterol averaged over Weeks 12-24
- Mean change from baseline in Hb levels between Weeks 18 to 24 in patients whose baseline hs-CRP $>$ ULN
- Average monthly IV iron use per subject during weeks 28-52
- Time to first RBC transfusion during the treatment
- Mean change in mean arterial pressure (MAP) averaged over Weeks 8-12

- Time to first exacerbation of hypertension (defined as [systolic BP ≥ 170 mmHg AND systolic BP increase from BL ≥ 20 mmHg] or [diastolic BP ≥ 110 mmHg AND diastolic BP increase from BL ≥ 15 mmHg]) during weeks 28 to 52

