11.2.1 Primary Analysis of Secondary Endpoints

The primary analysis for the secondary endpoints will be based on the PPS for the non-inferiority tests and FAS for the superiority tests for Ex-U.S. and FAS for U.S.

11.2.1.1 Hb

The first secondary efficacy endpoint for the US submission and the Ex-US submission will be the primary efficacy endpoint for the Ex-US submission and the US submission, respectively. The Ex-US secondary efficacy endpoint will use MMRM model described in 11.1.3.1. The US first secondary efficacy endpoints will use the same statistical analysis methodology for the primary efficacy endpoint for Ex-US.

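### SAP Table 5 and 11.2.1.1 misstate the ex-US gatekeeper test (Week 28–52 uncensored instead of Week 28–36 without rescue), and the hypertension test carries conflicting cut-offs and NI margins (1.8 and 1.3)

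*SAP*

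**What the plan says.** **The sequence.** SAP 11.2 promises overall two-sided 0.05 and states that "the secondary endpoints in the order that was specified in section 4.3 will be tested using a fixed sequence testing procedure". Table 5 then sets out the tests, with one comparison column per row. SAP 5.3 gives no multiplicity adjustment to tests outside the sequence.

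**Ex-US Test 1.** Table 5 gives "or the mean Hb change from baseline to the average level during the Evaluation Period, defined as Week 28 until Week 52 for Ex-U.S". SAP 11.2.1.1 says that the first secondary endpoints for the US and ex-US submissions "will be the primary efficacy endpoint for the Ex-US submission and the US submission, respectively". That makes the ex-US test the US primary, which does not censor values under rescue (SAP 11.1.1). Against this, SAP 4.3 has the evaluation period "defined as Week 28 until Week 36 without rescue therapy within 6 weeks prior to and during the evaluation period", on the PPS. Protocol 7.2 has "Mean Hb change from baseline to the average level during the Evaluation Period, defined as Week 28 until Week 36 without rescue therapy", also on the PPS. Protocol 8.4.3.2 adds that values under rescue "within 6 weeks prior to and during this 8-week evaluation period will be censored in the analysis".

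**Hypertension (last test).** SAP 4.3 and Table 5 use diastolic BP ≥110 mmHg. SAP 11.2.1.6 gives two definitions, ≥100 and then >100. Table 5 has superiority and non-inferiority with margin 1.8 in one row; 11.2.1.6 tests both with margin 1.3. SAP 4.4 lists a separate additional endpoint over the same weeks with systolic >170 and diastolic >100.

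**Lesser items.**
- SAP 4.3 places "The time to achieve the first hemoglobin (Hb) response defined by the primary endpoint for Ex-US" and "Proportion of patient exposure time (months) with Hb" ≥10 g/dL before LDL; Table 5 has neither, and SAP 11.3.1.1 treats the first as an additional analysis.
- SAP 11.2.1.3 adds superiority to a test that Table 5 lists as non-inferiority only.
- SAP 11.2.1.5 adds a 1 mmHg non-inferiority margin to the MAP test, which Table 5 lists as superiority.
- The IV iron formula in 11.2.1.4 runs from first dose to last visit, although its heading, 4.3 and Table 5 say Weeks 28–52.
- The US responder test is on ITT in 4.3 and on FAS in 11.2.1.

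**The concern.** A fixed sequence controls error because each step has one endpoint, one hypothesis and one margin, settled before anyone sees results. Here two steps have more than one current definition, and no text says which prevails. The trial is open label, so settling them late is harder to defend.

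Test 1 matters most because it gates every later ex-US claim. A programmer who follows Table 5 and 11.2.1.1 would open that sequence with an endpoint that the protocol does not define for this purpose. For hypertension, the cut-off decides who has an event and the margin decides what is claimed.

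**Working it through.** **1. The plan's own figures.** In one pre-fixed sequence, a false claim requires rejecting the first true null reached, so the family-wise error is 0.05 whichever single reading is used. Under the SAP 5.1 assumptions for the US primary (difference −0.30, margin −0.75, SD 1.25, 300 per arm), power is Φ(0.45 / (1.25 × √(2/300)) − 1.96) = Φ(4.41 − 1.96) = 99.3%. This agrees with the stated figure of at least 99%.

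**2. Ex-US Test 1, texts side by side.**

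| Text | Window | Values under rescue |
|---|---|---|
| SAP Table 5 | Week 28–52 | not stated |
| SAP 11.2.1.1 (as US primary) | Week 28–52 | kept |
| SAP 4.3 | Week 28–36 | excluded |
| Protocol 7.2, 8.4.3.2 | Week 28–36 | excluded |

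The PPS itself is not in doubt: SAP 11.2.1 assigns ex-US non-inferiority tests to it. Nor is the MMRM of 11.1.3.1 the problem, because SAP 11.3.1.2 uses the same model with rescue excluded.

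**3. What a late choice of window would cost.** Week 28–36 has three scheduled visits (28, 32, 36) and Week 28–52 has seven. The chance that at least one of the two tests passes at the margin is 1 − Φ₂(1.96, 1.96; r), where r is the correlation of the two window means. The documents give no between-visit correlation, so a range is assumed.

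| Assumed visit correlation | r, equal correlation | one-sided error | r, AR(1) | one-sided error |
|---|---|---|---|---|
| 0.3 | 0.866 | 3.67% | 0.692 | 4.19% |
| 0.5 | 0.926 | 3.38% | 0.738 | 4.08% |
| 0.7 | 0.964 | 3.12% | 0.813 | 3.86% |
| 0.9 | 0.990 | 2.83% | 0.926 | 3.38% |

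The nominal rate is 2.5%. These figures ignore the difference in rescue handling and apply only if the window is chosen after seeing results. The calculation in step 1, carried over to this test, gives 99.3% power at 300 per arm and Φ(0.45 / (1.25 × √(2/250)) − 1.96) = 98.1% at 250. The PPS size is not stated, so both arm sizes are assumptions.

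**4. Hypertension margins.** Taking both margins as hazard ratios from the Cox model, with 1:1 allocation and E events, SE(log HR) ≈ 2/√E. The largest observed HR that passes is margin × exp(−1.96 × 2/√E).

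| Assumed events | passes 1.3 up to | passes 1.8 up to |
|---|---|---|
| 50 | 0.75 | 1.03 |
| 100 | 0.88 | 1.22 |
| 200 | 0.99 | 1.36 |

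The ratio of the limits is 1.8/1.3 = 1.38 at any E. For 90% power at a true HR of 1, events needed are 4 × (1.96 + 1.28)² / (ln margin)²: 611 for 1.3 and 122 for 1.8. SAP Appendix 6 justifies only 0.75 g/dL and 0.15, so it supports neither.

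**5. Lesser items.** After Test 1, Table 5 runs LDL, CRP subgroup, IV iron, transfusion, MAP, hypertension. That is the order of SAP 4.3 with two endpoints left out.

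**The case against.** The best defence is that the intent can be recovered. Table 5 follows the 4.3 order and names one comparison per row, and SAP 11.2 introduces it as the sequence to be followed. A reader might infer two rival sequences; the natural reading is a subset of 4.3, and 11.3.1.1 agrees. One clarifying sentence is enough.

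A reader might also infer that, for the CRP-subgroup and MAP tests, the choice of reading decides whether later tests are reached. Table 5 already names the gate: non-inferiority for the former, superiority for the latter. Non-inferiority and superiority on one estimate are nested and do not by themselves inflate error.

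The IV iron formula is better read as a template than as a second endpoint, because SAP 11.3.4.3 reuses the same analysis for the second and third years. For transfusion, SAP 11.3.4.1 defines time to first transfusion and its censoring; only the model and the scale of the 1.8 margin are missing. The >100 wording in 11.2.1.6 matches the additional endpoint in 4.4 and may have been merged in from there. On the US population, SAP section 11 mentions both ITT and FAS, and 4.3 specifically names ITT for the responder test.

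All of that stands. It does not rescue Test 1: deferring to Table 5 fails when Table 5 is the text that contradicts the protocol, and 11.2.1.1 repeats the error, so it is not an isolated slip. Nor does it settle ≥110 against ≥100, or 1.8 against 1.3. Protocol 8.4.5 says when the SAP is finalised, not which of its readings applies.

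**Conclusion.** Two conflicts hold and should be fixed. Ex-US Test 1 is misstated in Table 5 and 11.2.1.1; the definition in SAP 4.3 and the protocol is clear. The hypertension test has no single event definition, margin or order of hypotheses. The remaining items are wording.

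A reader might infer that the sequence fails to control type I error. The documents do not support that: any one reading fixed in advance keeps two-sided 0.05. The 2.8–4.2% one-sided error for Test 1 requires a choice made after seeing results and rests on assumed correlations. The practical risk there is small, because power is high under either assumed arm size. Hypertension is last, so it cannot affect earlier tests; its factor of 1.38 between passing limits holds at any event count, while the HR ranges rest on assumed counts. Neither primary endpoint is affected.

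**What to change.** Before comparative data are reviewed:

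- **Test 1.** Correct Table 5 and 11.2.1.1 to Week 28–36, rescue-censored, PPS, keeping the 11.1.3.1 MMRM.
- **Hypertension.** Reconcile 4.3, 4.4, Table 5 and 11.2.1.6 so that the sequence has one definition and one non-inferiority margin, both chosen and justified by the sponsor. State the order of non-inferiority and superiority, and keep the additional endpoint in 4.4 separate.
- **Sequence.** State that Table 5 is operative and that the comparison in each row is the gate. State that the two omitted 4.3 endpoints are outside alpha control, and that the extra tests in 11.2.1.3 and 11.2.1.5 do not open the next step.
- **Details.** Restrict the IV iron numerator and denominator to Weeks 28–52. Name the time-to-event model and the scale of the 1.8 margin for transfusion. Use ITT for the US responder test.
- **Departures from protocol 8.4.3.2.** Highlight the significant ones, as protocol 8.4.5 requires, unless the SAP's front pages, which were not available here, already do so. Examples: LDL moved ahead of IV iron; the IV iron window; CRP-subgroup and transfusion tests added; proportion with hypertension exacerbation dropped; time to BP increase limited to Weeks 28–52 with a non-inferiority test added; time to Hb response moved to additional analyses.

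The cost is SAP wording and no new data. The one substantive task is the sponsor's justification of the hypertension definition and margin.

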#### 8.4.3.2 Secondary Efficacy Analyses

Once the null hypothesis has been rejected for the primary endpoint (for both, US [FDA] and ex-US submissions), the secondary endpoints below will be tested using a fixed sequence testing procedure, in order to maintain the overall two-sided Type I error rate at 0.05. If p-value from a test is  $< 0.05$ , the claim of superiority (or noninferiority) will be considered met and the test will progress to the next comparison in sequence as follows:

- **US (FDA) Submission:** The first secondary endpoint for US (FDA) submission is defined as the proportion of subjects who achieve a Hb response at two consecutive visits during the first 24 weeks of treatment, without rescue therapy within 6 weeks prior to the Hb response.

A Hb response is defined, using central laboratory values, as:

- $Hb \geq 11.0 \text{ g/dL}$  and a Hb increase from baseline by  $\geq 1.0 \text{ g/dL}$  in subjects whose baseline  $Hb > 8.0 \text{ g/dL}$ , or
- Increase in  $Hb \geq 2.0 \text{ g/dL}$  in subjects whose baseline  $Hb \leq 8.0 \text{ g/dL}$

The hypothesis to be tested for this efficacy analysis is:

$H_0: Hb \text{ response rate for subjects in the roxadustat arm} - Hb \text{ response rate for subjects in the epoetin alfa arm} \leq 15\%$

*Versus*

$H_1: Hb \text{ response rate for subjects in the roxadustat arm} - Hb \text{ response rate for subjects in the epoetin alfa arm} > 15\%$

A two-sided 95% CI for the difference of 2 responder rates (roxadustat minus epoetin alfa) based on the Miettinen & Nurminen approach adjusting for treatment and other stratification factors will be calculated and  $H_0$  will be rejected if the lower bound of the 95% CI is greater than -15%.

- **Ex-US Submission:** The first secondary endpoint for Ex-US submission is the mean change in Hb levels from baseline to the average level during the Evaluation Period, defined as Week 28 until Week 36. This analysis will be based on the PPS population.

The primary hypothesis to be tested for this efficacy analysis is:

$H_0: Hb \text{ mean change from baseline to the average level from Week 28 to Week 36 in the roxadustat arm} \leq Hb \text{ mean change from baseline in the epoetin alfa arm minus } 0.75 \text{ g/dL}$

*Versus:*

$H_1: Hb \text{ change from baseline to the average level of Week 28 to Week 36 in the roxadustat group} > Hb \text{ mean change from baseline in the epoetin alfa group minus } 0.75 \text{ g/dL}$

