The analysis will be repeated with Hb values under the influence of rescue therapy censored. Namely, set Hb to missing for Rescue Medication and 6 weeks afterwards (or 8 weeks if during the evaluation period).

Ex-US Submission: The primary efficacy endpoint for Ex-US submission is defined as the proportion of subjects who achieve an Hb response at two consecutive visits during the first 24 weeks of treatment, without rescue therapy within 6 weeks prior to the Hb response.

- A Hb response is defined, using central laboratory values, as: $Hb \geq 11.0$ g/dL and a Hb increase from baseline by ≥ 1.0 g/dL in subjects whose baseline $Hb > 8.0$ g/dL, or
- Increase in $Hb \geq 2.0$ g/dL in subjects whose baseline $Hb \leq 8.0$ g/dL

Rescue therapy for roxadustat treated subjects is defined as ESA rescue or RBC transfusion, and rescue therapy for epoetin alfa treated subjects is defined as RBC transfusion.

The hypothesis to be tested for the primary efficacy analysis is:

H_0 : Hb response rate for subjects in the roxadustat arm - Hb response rate for subjects in the epoetin alfa arm $\leq -15\%$

Versus

H_1 : Hb response rate for subjects in the roxadustat arm - Hb response rate for subjects in the epoetin alfa arm $> -15\%$

A two-sided 95% CI for the difference of 2 responder rates (roxadustat minus epoetin alfa) based on the Miettinen & Nurminen approach adjusting for treatment and stratification factors will be calculated and this null hypothesis will be rejected if the lower bound of the 95% CI is greater than -15%. Subjects who dropped out from the study without data for the assessment will be treated as non-responder.

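### Protocol 8.4.3.2 writes the null for the first US secondary test as a difference of at most +15%, while the same section rejects it against -15%

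*SAP*

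**What the plan says.** Protocol 8.4.3.2 puts the responder rate first in the US fixed sequence. With the difference taken as roxadustat minus epoetin alfa, the null hypothesis ends "response rate for subjects in the epoetin alfa arm} \leq 15" percent (the typesetting code stands for at most) and the alternative ends "response rate for subjects in the epoetin alfa arm} > 15" percent. A few lines later the null "will be rejected if the lower bound of the 95% CI is greater than -15" percent.

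SAP 11.1.2 states the same endpoint for the Ex-US submission, where it is primary, with a negative threshold: "Hb response rate for subjects in the epoetin alfa arm $\leq -15" percent.

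SAP 11.2, Table 5, Test 1 is a row labelled as non-inferiority. For the responder endpoint it says "The non-inferiority margin for the difference of responder analysis between groups is 0.15". For the haemoglobin endpoint, in the same cell, it says "The non-inferiority margin for the difference of average of Change in Hb values between groups is - 0.75 g/dL". The table writes out no null hypothesis for either.

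SAP 11.2.1.1 adds: "The US first secondary efficacy endpoints will use the same statistical analysis methodology for the primary efficacy endpoint for Ex-US".

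**The concern.** Read as written, the protocol's hypotheses ask roxadustat to beat epoetin alfa by more than 15 percentage points, whereas the rejection rule asks only that it be no more than 15 points worse. The two thresholds are 30 points apart.

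This is a confirmatory threshold, and it sits at the head of the US secondary sequence, so every later US test depends on it. In both documents the sequence advances when a p-value falls below 0.05. A p-value is computed against a stated null, so the sign of that null matters even though the confidence-interval rule is written correctly. Someone programming the p-value from the protocol's hypothesis lines would obtain a result at odds with the interval.

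**Working it through.** **Where each sign appears, for the same endpoint and the same direction of difference**

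- Power statements, Protocol 8.1 (and synopsis) and SAP 5.1: -15%.
- Ex-US hypotheses and rejection rule, Protocol 8.4.3.1 and SAP 11.1.2: -15%.
- US rejection rule, Protocol 8.4.3.2: -15%.
- US hypotheses, Protocol 8.4.3.2: +15%.
- SAP Table 5 and SAP Appendix 6: 0.15, as a magnitude.

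The +15% hypotheses occur in one place only.

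**Inputs.** 80% response in both arms, at least 600 subjects and a -15% margin (Protocol 8.1, SAP 5.1); 1:1 allocation, so 300 per arm; two-sided 5% (SAP 5.3), so 2.5% in the direction tested and a critical value of 1.96.

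**1. The plan's own figure.** Standard error = sqrt(2 × 0.8 × 0.2 / 300) = 0.0327. Power against -15% = Phi(0.15/0.0327 - 1.96) = Phi(4.593 - 1.96) = Phi(2.633) = 99.6%. The stated figure of at least 99% reproduces.

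Two checks agree:

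- With the variance taken at the null boundary (80% against 65%), power is 99.3%.
- A 40,000-replicate simulation of the unstratified Miettinen-Nurminen score test gives 99.6%, with one-sided type I error of 2.5% at the -15% boundary.

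**2. The null as written, tested against +15%.** Power = Phi(-4.593 - 1.96) = Phi(-6.553), about 3 × 10^-11. With epoetin alfa at 80% the largest possible difference is +20 points. The observed difference would have to reach about +19.6 points at 300 per arm, or +18.4 at 600 per arm. That is superiority by a margin, not non-inferiority.

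**3. The null as written, tested with the rule as written.** Put the truth on the written boundary, 95% against 80%. Standard error = sqrt((0.95 × 0.05 + 0.8 × 0.2)/300) = 0.0263. The chance that the lower bound exceeds -15% is Phi((0.15 + 0.15)/0.0263 - 1.96) = Phi(9.45), effectively 100%. The rule therefore gives no error control for the null that precedes it.

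**4. p-value against interval.** Suppose the observed rates are 80% in each arm. The test statistic is +4.59 against -15% and -4.59 against +15%. The one-sided p-value is close to 0 in the first case and close to 1 in the second, from the same data.

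**5. After correction.** With the null at -15%, step 1 applies unchanged. The rule is met when the observed difference is above about -8.2 points at 300 per arm (control at 80%).

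**The case against.** The strongest defence is that no analyst following the SAP would run the wrong test. SAP 11.2.1.1 refers the US endpoint to the Ex-US method, which SAP 11.1.2 sets out with -15% in the hypotheses and in the rule. Protocol 8.4.5 leaves analysis detail to the SAP. The only rejection rule written for this test anywhere is the -15% one. This stands, and it limits the consequence. It does not remove the contradiction inside Protocol 8.4.3.2.

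Three stronger readings are tempting, and the documents do not support them.

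- A reader might infer that Table 5 itself carries the wrong sign. It does not: an unsigned margin in a row labelled non-inferiority is a normal way to state a magnitude, and Appendix 6 derives the margin in that form. Its only flaw is that the neighbouring haemoglobin margin is signed.
- A reader might infer that the US sequence would stop at Test 1. That needs a rule requiring the lower bound to exceed +15%, and no such rule is written.
- A reader might infer that the confidence-interval rule is the only place with -15%. Across the two documents it is not, as the list in the working shows.

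A minus sign can also be lost when text is read out of a PDF, so the source page should be checked. Loss seems unlikely: the sign is absent from both US hypothesis lines but present in the rule beneath them and in the matching Ex-US hypotheses.

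**Conclusion.** The sign error in the US hypotheses of Protocol 8.4.3.2 is real, subject to that check of the source page. It leaves a confirmatory null and its rejection rule describing different tests, with power of about 0 and 99.6% respectively under the plan's assumptions. The practical effect is small because the intended test, -15%, can be recovered from the rest of the protocol and from SAP 11.2.1.1. It still deserves correction, because it concerns a decision threshold and because the sequence advances on a p-value.

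The power figures assume 80% response in both arms, 300 per arm and no loss of subjects. The documents give no loss rate for this calculation. If, as an assumption, 10% to 20% were lost (270 to 240 per arm), power against -15% would be 99.2% to 98.4%. None of this bears on the sign.

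**What to change.** In Protocol 8.4.3.2, write H0 as a difference (roxadustat minus epoetin alfa) of at most -15% and H1 as a difference above -15%. If the protocol is not to be amended, state the correction in the SAP, which Protocol 8.4.5 already names as a place to flag significant changes to the protocol's analyses.

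In SAP Table 5, Test 1, give the responder margin as -0.15 (roxadustat minus epoetin alfa; lower bound of the two-sided 95% CI must exceed -0.15), to match the signed haemoglobin margin beside it. It would also help to say there that the p-value used to advance the sequence is computed against that null.

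The cost is wording only. Sample size, stated power and the confidence-interval rule stay as they are.
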